15.2.2 Safety Analyses

All safety analyses will be conducted in the Safety population.

Verbatim descriptions of AEs will be coded using MedDRA. Summary tables will be provided for all treatment-emergent adverse events (TEAEs). A treatment-emergent AE is defined as any AE that newly appeared, increased in frequency, or worsened in severity following initiation of

study drug. The number and percentage of subjects reporting a TEAE in each treatment group will be tabulated by system organ class and preferred term; by system organ class, preferred term, and severity; and by system organ class, preferred term, and relationship to study drug. The number and percentage of subjects reporting an SAE and reporting a TEAE leading to premature discontinuation of study drug in each treatment group will be summarized by system organ class and preferred term. For all analyses of TEAEs, if the same AE (based on preferred term) is reported for the same subject more than once, the AE is counted only once for that preferred term and at the highest severity and strongest relationship to study drug. Abnormal physical examination results are recorded as AEs (when appropriate) and thus, physical exam data will not be summarized in a table.

Descriptive statistics for hematology, chemistry, coagulation and where applicable, urinalysis, values and the change from baseline will be summarized by treatment group and time point, and for the overall worst value post-baseline. Toxicity grades will be determined based on the modified DMID criteria and shift tables will be presented. The number and percentage of subjects with at least a two grade increase from baseline (based on DMID criteria) will be summarized by treatment arm.

Descriptive statistics of the change from baseline for vital signs will be summarized by treatment group and time point. Abnormal values, identified by threshold values defined in the SAP, will be summarized.

15.3 Sample Size Considerations

This study is designed to demonstrate non-inferiority of eravacycline to ertapenem in the co-primary efficacy measures of responder outcome at the EOI and TOC visits in the micro-ITT population. An NI margin of 10% will be used which is based on historical data regarding the treatment effect of antibiotics. A 10% NI margin for the efficacy measure of responder outcome is robust and can sufficiently confirm a clinically meaningful treatment effect of eravacycline in the treatment of cUTI.

The sample size calculation is based on ensuring sufficient power for the co-primary efficacy outcomes for the FDA as well as the co-primary efficacy outcomes for the EMA (which are secondary efficacy outcomes for the FDA). Using a 10% non-inferiority margin, one-sided alpha of 0.025, 80% power, response rates at TOC of 71% in the eravacycline group and 72% in the ertapenem group, and the sample size methodology of Farrington and Manning, a total of 395 subjects per arm in the micro-ITT population is required. This sample size provides >90% power for the response rates at EOI assuming the response rates are 93% and 94% in the eravacycline and ertapenem groups, respectively. A sample size of approximately 1200 randomized subjects should

provide sufficient numbers for this study, assuming 66% of enrolled subjects will meet the requirements for inclusion in the micro-ITT population.

For the EMA, it is assumed that 65% of the randomized subjects will be in the micro-MITT population and 60% in ME population. The microbiological success rates at TOC are assumed to be 79% and 82% in both treatment groups in the micro-MITT and ME populations, respectively. With these assumptions, using a non-inferiority margin of 10%, a one-sided alpha of 0.005, and the sample size methodology of Farrington and Manning, there is at least 80% power to show non-inferiority for the co-primary efficacy outcomes. The power calculations are summarized in Table 4 below based on a total of 1200 randomized subjects:

Table 4: Assumptions for Sample Size Calculations

Outcome/Population	Alpha level (one-sided)	Evaluability Rate	Outcome Rates		Total N	Power
			ERV	ERT		
FDA Outcomes						
Responder at EOI/micro-ITT	0.025	66%	93%	94%	790	>99%
Responder at TOC/micro-ITT	0.025	66%	71%	72%	790	80.0%
EMA Outcomes						
Clinical Cure at TOC/micro-MITT	0.005	65%	79%	79%	780	79.8%
Clinical Cure at TOC/ME	0.005	60%	82%	82%	720	84.7%

ERV=Eravacycline; ERT=Ertapenem

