For the calculation of sample size it is assumed that 66% of the randomized subjects will be in the micro-ITT population. It is also assumed that the responder rates (clinical cure and microbiological success) at EOI will be 93% and 94% in the eravacycline group and the ertapenem group, respectively and at TOC will be 71% and 72% in the eravacycline group and ertapenem group, respectively. For the EMA, it was assumed that 65% of the randomized subjects will be in the micro-MITT population and 60% in the ME population. The microbiological success rates at TOC are assumed to be 79% and 82% in both treatment groups in the micro-MITT and ME populations, respectively. With these assumptions, utilizing a 10% non-inferiority margin, and the sample size methodology of Farrington-Manning, 790 subjects (395 subjects per group) are required in the micro-ITT population and a total of 1200 subjects will be randomized. This sample size provides at least 80% power for the co-primary efficacy outcomes at EOI and TOC in the micro-ITT population as well as for the co-primary outcomes for the EMA.

Safety

Safety analyses will be conducted on the safety population. Subjects will be analyzed according to the treatments received.

Adverse Events

Verbatim descriptions of adverse events (AEs) will be mapped to Preferred Terms and System Organ Classes using Medical Dictionary of Regulatory Activities (MedDRA) and tabulated by treatment arm. The number and percentage of subjects who experience treatment-emergent AEs and serious AEs will be presented by reporting levels for System Organ Class and Preferred Term. Each subject will be counted once for each level of reporting. Tabulations by severity and by relationship to study drug, as reported by the Investigators, will also be provided. Deaths and premature discontinuations from study drug due to an AE will be identified.

Laboratory Data

Hematology, chemistry, coagulation, and urinalysis (where applicable) data will be summarized using shift tables based on toxicity criteria, change from baseline, and the number and percentage of subjects with clinically notable values. Clinically notable values will be specified in the Statistical Analysis Plan.

Other Safety Data

Physical examination data will be reported (as warranted) and analyzed as adverse events. Vital signs will be summarized using descriptive statistics for change from baseline and percentage of subjects with an abnormal value as defined in the SAP.

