Efficacy Assessments

Responder rates will be determined for each treatment arm overall and for the randomization stratification factors: (1) primary site of infection (pyelonephritis and normal urinary tract anatomy vs. all other diagnoses) and (2) receipt of a single dose of effective non-study antibiotics for the acute cUTI within 72 hours prior to randomization. The responder rate will be determined as the number of subjects with clinical cure (i.e., complete or significant improvement of signs or symptoms such that no further systemic antibiotic treatment is required) and microbiological success at the respective visit divided by the number of subjects in the analysis population (i.e., overall or by randomization strata). A two-sided 95% CI around the difference in the eravacycline and ertapenem responder rates will be determined using the Miettinen and Nurminen method. If the lower bound of the 95% CI for the difference in responder rates at EOI and TOC in the micro-ITT population is above -10% for both time points, noninferiority of eravacycline to ertapenem will be concluded.

For the EMA, the microbiological success rate will be determined as the number of subjects with microbiological success at the respective visit divided by the number of subjects in the analysis population. Microbiological success rates at TOC will be determined, along with two-sided 99% CIs, by treatment arm for subjects in the micro-MITT and ME populations. If the lower bound of the 99% CI for the difference in microbiological success rates at TOC is above -10% for both the micro-MITT and ME populations, noninferiority of eravacycline to ertapenem will be concluded.

Clinical outcome and microbiological outcome will be summarized by treatment group, time point and analysis population. Two-sided 95% CIs for the difference between treatment groups in clinical cure and microbiological success will be provided.

Microbiology

Purified bacterial pathogens aerobically cultured from urine using a calibrated loop to identify a quantitative count of bacteria at a lower limit of 10^3 CFU/mL and aerobic and anaerobic blood culture pathogens will be evaluated for susceptibility and the emergence of resistance to study drugs and overgrowth of non-susceptible organisms at a central laboratory.

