4. GENERAL STATISTICAL METHODS

4.1. Sample Size Justification

This study is designed to demonstrate NI of eravacycline to ertapenem in the co-primary efficacy measures of responder outcome at the EOI and TOC visits in the micro-ITT population. An NI margin of 10% will be used which is based on historical data regarding the treatment effect of antibiotics. A 10% NI margin for the efficacy measure of responder outcome is robust and can sufficiently confirm a clinically meaningful treatment effect of eravacycline in the treatment of cUTI.

The sample size calculation is based on ensuring sufficient power for the co-primary efficacy outcomes for the FDA as well as the co-primary efficacy outcomes for the EMA (which are secondary efficacy outcomes for the FDA). Using a 10% NI margin, one-sided alpha of 0.025, 80% power, response rates at TOC of 71% in the eravacycline group and 72% in the ertapenem group, and the sample size methodology of Farrington and Manning, a total of 395 subjects per arm in the micro-ITT population is required. This sample size provides >90% power for the response rates at EOI assuming the response rates are 93% and 94% in the eravacycline and ertapenem groups, respectively. A sample size of approximately 1200 randomized subjects should provide sufficient numbers for this study, assuming 66% of enrolled subjects will meet the requirements for inclusion in the micro-ITT population.

For the EMA, it is assumed that 65% of the randomized subjects will be in the micro-MITT population and 60% in ME population. The microbiological success rates at TOC are assumed to be 79% and 82% in both treatment groups in the micro-MITT and ME populations, respectively. With these assumptions, using an NI margin of 10%, a one-sided alpha of 0.005, and the sample size methodology of Farrington and Manning, there is at least 80% power to show NI for the co-primary efficacy outcomes. The power calculations are summarized in [Table 3](#) based on a total of 1200 randomized subjects.

Table 3 Assumptions of Sample Size Calculations

Outcome/Population	Alpha level (one-sided)	Evaluability Rate	Outcome Rates		Total N	Power
			ERV	ERT		
FDA Outcomes						
Responder at EOI/micro-ITT	0.025	66%	93%	94%	790	>99%
Responder at TOC/micro-ITT	0.025	66%	71%	72%	790	80.0%
EMA Outcomes						
Microbiological Success at	0.005	65%	79%	79%	780	79.8%

TOC / micro-MITT						
Microbiological Success at TOC / ME-TOC	0.005	60%	82%	82%	720	84.7%

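### The power printed for the EMA outcome in the ME population (84.7%) belongs to N = 780; at the stated N = 720 it is 81.1%, and the text's 80% floor for the EMA outcomes conflicts with the table's own 79.8%.

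*Protocol*

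**What the plan says.** Protocol 15.3 sets the EMA calculation up "using a non-inferiority margin of 10%, a one-sided alpha of 0.005, and the sample size methodology of Farrington and Manning". It assumes success at TOC of 79% in both arms of the micro-MITT population (65% of those randomized) and 82% in both arms of the ME population (60%). It concludes that "there is at least 80% power to show non-inferiority for the co-primary efficacy outcomes", and adds: "The power calculations are summarized in Table 4 below based on a total of 1200 randomized subjects".

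The two EMA rows of that table read:

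| Population | Alpha (one-sided) | Evaluable | Rates | Total N | Power |
|---|---|---|---|---|---|
| micro-MITT | 0.005 | 65% | 79% / 79% | 780 | 79.8% |
| ME | 0.005 | 60% | 82% / 82% | 720 | 84.7% |

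SAP 4.1 states that "there is at least 80% power to show NI for the co-primary efficacy outcomes", and its Table 3 carries the same numbers. The SAP labels the ME row "Microbiological Success at TOC / ME-TOC", whereas the protocol labels it "Clinical Cure at TOC/ME". The protocol synopsis says "This sample size provides at least 80% power for the co-primary efficacy outcomes" and extends this to the EMA outcomes. The synopsis also gives the EMA decision rule: the lower 99% limit must lie above -10% "for both the micro-MITT and ME populations, noninferiority of eravacycline to ertapenem will be concluded".

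**The concern.** The two EMA rows share alpha, margin and method. The ME row has a higher success rate, which raises power, but 60 fewer subjects, which lowers it. A gain of almost 5 points over micro-MITT looked too large for that trade.

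The figure matters because it is the plan's stated reserve for an outcome that must succeed for the EMA claim. At 84.7% the ME analysis appears able to absorb a fair loss of evaluable subjects. If the true figure is near 80%, it cannot. The blinded checks planned at about 800 subjects (Protocol 9.1 and 15.4, SAP 4.7) look at the micro-ITT proportion and the overall responder rate, not at the ME proportion. A separate EMA SAP is announced in SAP 1.1.1 and could inherit the figure.

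The statement of at least 80% power for both EMA outcomes also sits directly above a table that prints 79.8% for one of them.

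**Working it through.** **Inputs (Protocol 15.3; 1:1 allocation from Protocol 11.2.2).** Margin m = 0.10; one-sided alpha 0.005 (z = 2.5758) for the EMA rows and 0.025 (z = 1.9600) for the FDA rows. Arm sizes are half the table's Total N: 395, 390 and 360. N = 720 is not a misprint, since 0.60 × 1200 = 720.

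**Formula (Farrington-Manning, n per arm).** With assumed rates p1, p2, and q1, q2 the maximum-likelihood rates constrained to q1 − q2 = −m:

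- s0 = √{[q1(1−q1) + q2(1−q2)]/n}
- s1 = √{[p1(1−p1) + p2(1−p2)]/n}
- power = Φ{(p1 − p2 + m − z·s0)/s1}

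**Step 1: reproduce the other three rows.**

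| Row | n per arm | q1, q2 | s0 | s1 | Power | Printed |
|---|---|---|---|---|---|---|
| FDA EOI, 93/94% | 395 | 0.8614, 0.9614 | 0.01991 | 0.01754 | 99.8% | >99% |
| FDA TOC, 71/72% | 395 | 0.6603, 0.7603 | 0.03208 | 0.03212 | 80.1% | 80.0% |
| micro-MITT, 79/79% | 390 | 0.7316, 0.8316 | 0.02937 | 0.02917 | 79.8% | 79.8% |

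All three agree, to within 0.1 point where an exact figure is printed, so the method is identified.

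**Step 2: the ME row as printed.** For 82/82%, q1 = 0.7598 and q2 = 0.8598.

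- n = 360: s0 = 0.02902, s1 = 0.02864; (0.10 − 2.5758 × 0.02902)/0.02864 = 0.882; power **81.1%**.
- n = 390: s0 = 0.02788, s1 = 0.02751; (0.10 − 2.5758 × 0.02788)/0.02751 = 1.025; power **84.7%**.

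The printed value is the N = 780 result.

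**Step 3: can anything else explain 84.7% at 360 per arm?**

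- Other forms of the calculation at alpha 0.005: restricted standard error throughout 80.8%, Miettinen-Nurminen factor 81.1%, unpooled variance 82.0%, continuity-corrected 79.4%, exact enumeration 81.4%. None is close.
- Another alpha: 0.01 gives 87.2% and 0.025 gives 93.4%. Solving for 84.7% needs 0.0074, which is not stated.
- Another success rate: solving for 84.7% needs 83.9%. Text and table both say 82%.

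**Step 4: the real reserve.** ME power is 79.9% at 351 per arm and first reaches 80% at 352, or 704 in total. The reserve is 720 − 704 = 16 subjects, and evaluability can fall from 60% only to 704/1200 = 58.7%.

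**Step 5: the 80% statement.** Micro-MITT first reaches 80% at 392 per arm (784 in total), four more subjects than the 780 planned. Both populations must pass, so joint power under this method cannot exceed 79.8%. The documents give no correlation between the two tests. Taking ME as nested in micro-MITT and treating the two test statistics as bivariate normal:

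| Assumed correlation | Joint power |
|---|---|
| 0.90 | 75.5% |
| 0.95 | 76.9% |
| 0.98 | 78.2% |

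**Step 6: the total.** The FDA TOC row alone requires 790/0.66 = 1197 randomized, so 1200 stands.

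**The case against.** The arithmetic of the ME cell cannot be defended, but its weight can be disputed.

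- Nothing operational changes: ME power stays above 80%, the FDA outcome drives the total, and the EMA outcomes are secondary for the FDA. This stands, and it makes the point a reporting correction.
- The conflict between 79.8% and the 80% statement is four subjects in a trial of approximately 1200, and exact enumeration of the unstratified test gives 80.1% for micro-MITT. This also stands. It is a mismatch of wording, although 79.8% is the figure by the method the plan names.
- The documents never claim a joint power, and the 75% to 78% range depends on the correlation chosen: 0.80 gives 73.5%, and with no assumption the bounds are 60.9% and 79.8%. That is fair. Only the ceiling of 79.8% is free of assumptions, so a joint figure should be optional and carry its assumption.
- ME is a subset of micro-ITT, so an increase triggered by a low micro-ITT proportion would raise ME numbers too. This is right as far as it goes. What escapes the checks is a fall in ME relative to micro-ITT, through protocol deviations or uninterpretable TOC cultures.
- That the micro-MITT size was carried into the ME row is an inference. What is established is that the number fits N = 780 and does not fit N = 720.

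**Conclusion.** The concern holds. By the plan's own method and inputs, ME power is 81.1%, not 84.7%: an overstatement of 3.6 points that shrinks the reserve over 80% from 4.7 points to 1.1. The 80% floor claimed for the EMA outcomes is contradicted by the 79.8% in the same table, by a trivial amount. The error should be fixed, but it does not threaten the design: the corrected ME power still exceeds 80% and the sample size is unaffected.

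The ME figure rests only on stated inputs and Farrington-Manning without stratification. Protocol 15.2.1 plans a stratified interval for the EMA analysis, which neither the plan's calculation nor this one models. The joint range of 75.5% to 78.2% rests in addition on an assumed correlation of 0.90 to 0.98.

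**What to change.** 1. In Protocol Table 4 and SAP Table 3, change the ME power from 84.7% to 81.1%.
2. In the protocol synopsis (Sample Size Estimation), Protocol 15.3 and SAP 4.1, replace the 80% statement for the EMA outcomes with 79.8% for micro-MITT and 81.1% for ME. Leave the FDA statement as it is.
3. In Protocol Table 4, relabel the two EMA rows from clinical cure to microbiological success, to match the adjacent text and SAP Table 3. This label does not affect the power.
4. Optionally, add that joint power for the EMA pair is roughly 75% to 78%, assuming that ME is nested in micro-MITT and that the two tests correlate at about 0.90 to 0.98.

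Items 1 to 3 cost two table cells, three sentences and two row labels; item 4 would add one sentence. The stated ME power becomes less favourable. No patients are added, and the sample size, test, margin and decision rule stay as they are. The corrected figures should also go into the separate EMA SAP.

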15.4 Data Safety Monitoring Board (DSMB)

A DSMB will meet after approximately 300 subjects have reached EOT in the study, and again after approximately 800 subjects have reached EOT. The DSMB will advise the Sponsor regarding the continuation, modification, or termination of the study. The DSMB may meet at other timepoints as necessary.

The DSMB will have access to the following data:

- Incidence of AEs (overall and drug-related)
- Listing of SAEs
- Premature discontinuations from study drug due to an AE
- Safety laboratory data

The DSMB may be provided with additional data if requested.

The DSMB and Sponsor will conduct an assessment of the actual number of subjects in the micro-ITT population, which will be made following the completion of treatment (EOT) of approximately 800 subjects. If there is less than the expected proportion of subjects in the micro-ITT population, the sample size will be adjusted as needed (without a formal protocol amendment) to provide a sufficient number of evaluable subjects.

In addition, the DSMB will conduct an assessment of the overall (aggregated across treatment groups) blinded responder rate (clinical cure and microbiological success) at the TOC visit following the completion of approximately 800 subjects. If the overall blinded responder rate is less than the rate used in the sample size calculation for the eravacycline group, the sample size will be increased as needed (without a formal protocol amendment) to ensure 80% power. The sample size will not be decreased if the overall blinded responder rate is greater than the rate used in the sample size calculation.

A charter for the DSMB, comprised as a separate document, will be available prior to the first meeting. Recommendations from the DSMB will be made in writing and provided to the Sponsor after each data review.

16. STUDY DRUG MATERIALS

16.1 Study Drug Nomenclature

TP-434 is the active ingredient in eravacycline drug product. The chemical name of TP-434-046 (di HCl salt form) is: [(4S,4aS,5aR,12aS)-4-(dimethylamino)-7-fluoro-3,10,12,12a-tetrahydroxy-1,11-dioxo-9-(2-(pyrrolidin-1-yl)ethanamido)-1,4,4a,5,5a,6,11,12a-octahydrotetracene-2-carboxamide] di-hydrochloride. The molecular formula for the free base is C₂₇H₃₁FN₄O₈, and the molecular weight is 558.56. Eravacycline is a yellow to orange solid that is soluble in water.

16.2 Study Drug Preparation

16.2.1 Reconstitution of IV Study Drug

A trained, unblinded pharmacist/designee will prepare intravenous study drug. Detailed instructions for the preparation of study drug are provided in the Pharmacy Manual.

The eravacycline drug product will be reconstituted using sterile water for infusion (WFI) and will be diluted using 0.9% NaCl. Reconstituted eravacycline should be a "clear yellow solution" with no visible particulates in the vial. Once WFI is added to eravacycline vials, swirl each vial gently until the drug dissolves completely (it should take approximately 1 to 2 minutes to achieve a clear yellow solution).

The unblinded pharmacist/designee will provide the Investigator with ready-to-use blinded infusion solutions covered with an opaque bag for administration at scheduled study drug infusion times. It is the responsibility of the unblinded pharmacist/designee to maintain the blind of the infusion solutions.

16.2.2 Infusion Administration

In the event of discomfort and/or pain due to infusion, the following actions can be taken for the infusion which caused the reaction after confirming vein patency and flow at the Investigators' request (in the recommended order):

- Decrease concentration (by doubling volume, as long as infusion volume does not exceed 500 mL per IV bag)
- Increase length of infusion time (by doubling infusion time, up to 120 minutes per IV bag)

16.3 Study Drug Storage

Study drugs must be stored in a restricted access area under the storage conditions indicated on the product label and in the Pharmacy Manual. For further details, please consult the Pharmacy Manual.

